6.6.2 In-Person On-Site/Telephone Contact

Study staff for sites requiring on-site visits will contact participants via telephone on Day 7 and 28 (all others performing remote monitoring will contact participants on Day 7, 28, and 35) as described in the Schedule of Events (Table 4) and confirm participants' current health status including presence of any COVID-19 symptoms (Appendix 2; Appendix 3), in addition to any ER or hospital visits that might have occurred as a result of COVID-19. Participants will also be asked about any challenges with administration or any AEs they may have experienced.

Participants who are hospitalized for any reason and are unable to attend their on-site visit / telehealth assessment or complete their daily diary should have their emergency contact notify study staff as soon as possible. Participants that are hospitalized for COVID-19 only are considered treatment failures. Participants that are hospitalized for any other reason may stay on the study at the discretion of the Investigator.

Follow-up visits (end of study and early termination assessments) will be performed preferably on-site (in countries where remote only conduct is not allowed), but if the participant is hospitalized, in quarantine or unable to visit the site in-person for any reasonable cause as per investigators' judgement, these visits may be performed remotely and will not be considered a protocol deviation. Follow-up of all adverse events must be completed as described in the protocol Section 7.

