9.2 Determination of Sample Size

For an annualized infection rate of 3% in the placebo arm (daily incidence = 0.000075), and assuming a true hazard ratio of 0.15 implying protective effect of NONS equivalent to a vaccine efficacy of 85%, a sample size of 11,480 participants randomized 1:1 (NONS:Placebo) and available in the modified intent-to-treat (mITT) population will provide 90% power to demonstrate superiority of NONS to placebo in preventing COVID-19 infections reported through 28 days, based on Cox regression model and a 2-sided 0.05-level test (Schoenfeld 1983). The expected number of events in the two arms is 2 and 10 for the NONS and placebo groups respectively. This further assumes 25% censoring during the 28-day period (1.05% loss per day).

Sample size calculations conducted under version 1.0 of the protocol (dated April 27, 2021) used estimates of annualized case rates as listed in Table 2. At that time, the recent estimated annualized infection rate based on confirmed cases ranged from 2.2 through 3.9% in select Canadian provinces, though there was considerable variability, and these rates underestimate the true infection rates considering those untested. The US and other nations may have substantially higher infection rates and require fewer subjects to be randomized.

In particular, for the Czech Republic, Slovakia, and Sri Lanka, the reported annualized rates are between 0.14% and 8.23%, 0.07% and 7.27%, and 1.48% and 6.18% respectively over the period of May 1, 2021, to July 31, 2021. We are therefore likely to have sufficient power to conduct this study in those countries.

The maximum number of participants who will be randomized is 13,000, in order to achieve a maximum of 11,480 participants initiating their randomized treatment assignment and entering the mITT population. If the infection rate is higher than assumed here, enrollment and randomization will be closed if the total number of COVID-19 events in the mITT population exceeds 18 cases, 50% more than the number expected for 90% power. This inflation accounts for the increased infection rate and the consequent increased risk of infection between the time of randomization and time of initiation of study treatment due shipping times.

Table 2 Daily COVID-19 Counts

Population	Estimated annualized rate in February 2021	Equivalent date based on study in control arm	assumption	Days Daily Confirmed case counts exceeded 3% / 4% annualized rate		

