9.5 Analysis of Efficacy

9.5.1 Primary Efficacy Analysis

The primary efficacy objective is to demonstrate that NONS product reduces the risk of COVID-19 infection. The associated null hypothesis is that the hazard ratio (HR) of NONS relative to placebo is greater than 1, or H_0 : $HR \ge 1$, or equivalently in terms of a vaccine efficacy, H_0 : $VE \ge 0$ where vaccine efficacy is calculated as VE = 100% x (1-HR). The HR will be estimated using a Cox proportional hazard regression model with a fixed effect only for treatment arm. Due to the small, expected event rate (see the Section 9.2), incorporation of additional fixed effects may not be possible. However, as a sensitivity analysis, a stratified Cox model using randomization strata (≥ 65 , <65 at increased risk, < not at increased risk) will also be fit. Similarly, age-group (\ge /<65) and region-specific models will be fit, aggregating adjacent provinces, states, or larger geographies to enable model convergence and evaluate, to the extent possible, whether differences exist.

The primary analysis will be executed in the mITT data set and count all cases occurring starting from the day after participants begin administering study treatment.

For all models, a 2-sided score-based 95% confidence interval (CI) and 2-sided p-value for the effect of NONS will be calculated.

The estimand of the primary analysis is a treatment policy strategy and will consider intercurrent events as censored. Specifically, participants who stop administering NONS for any reason, stop submitting data to the electronic patient-reported outcomes (ePRO) system, do not submit paper diaries, or are unreachable by telephone contact, will be censored on the day of their last ePRO clinical status submission or last available documented day on paper diary (ie, the last day confirming no positive COVID-19 test). Participants who submit COVID-19 test results following Day 28, will be censored at Day 28. Participants submitting a COVID-19 test result on or prior to Day 28 will be considered to have reached the primary endpoint on the day that the specimen (ie, nasal swab) is collected, not the date of the test. Positive test results obtained within 48 hours of randomization will be considered infected at randomization and not counted as events.

The Cox model will be fit to the following sets (if different) as sensitivity analyses:

- mITT set counting all cases after randomization,
- PP set counting cases after first administration,

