13 APPENDICES

Appendix 1 Schedule of Events

Table 4 Schedule of Events

	Screening a Baseline	Daily on TX	Early TX Day	Last Tx Day	Post-Tx Follow-up		
Assessments			Phone Assessment 1	Phone Assessment 2	Phone Assessment 3	ET	
Visit Type (per specific country regulatory legislation)	Remotely or On-Site	Remotely	Remotely	Remotely	Remotely or On-Site	Remotely or On-Site	
Study Day	-7 to 1	1-35 ^d	7+3	28 +2	End of Study 35±3		
Participant Informed Consent (Virtual, if applicable/respective country) b	X						
Demographics (Virtual, if applicable/respective country)	X						
Medical History (Virtual, if applicable/respective country)	X						
Clinical Exam including Vitals (Virtual, if applicable/respective country)	X				X	X	
Pregnancy Test (Urine) ^c	X				X	X	
Concomitant Medications ^d	X	X	X	X	X	X	
Randomization	X						
Study treatment instructions ^e	X		X				
COVID related symptom assessment ^f			X	X	X	X	
NONS Self Administration ^g		X	X	X			
Questionnaire (online/paper) h		Xi	X	X	X	X	
Adverse Events		X	X	X	X	X	
Study Drug Accountability/Compliance		X	X	X		X	
Report if tested positive for COVID-19 infection		X	X	X	X	X	
Report need for Hospitalization/ER Visit for COVID-19 related sequelae		X	X	X	X	X	

Abbreviations: ER=emergency room; ET= early termination; NONS= nitric oxide nasal spray; Tx=treatment.

NONS (nitric oxide nasal spray)
Clinical Trial Protocol: COVID-NONS-04

- ^a Screening and baseline are to be taken within 7 days but may be taken at the same assessment. Post-Treatment Follow-up visits (end of study and ET) may be performed remotely. For countries requiring an in-person visit, these will be performed on-site, unless the participant is hospitalized, in quarantine or unable to visit the site for any reasonable cause as per the investigators' judgement; these visits may then be performed remotely and will not be considered a protocol deviation. Follow-up of all adverse events must be completed as described in the protocol Section 7.
- Participants will be asked to designate an emergency contact who will also sign informed consent. In the event the participant is hospitalized and cannot complete their treatment diary or questionnaire emergency contacts will be encouraged to provide symptoms on behalf of a participant in a COVID-19 symptoms list Diary (Appendix 2).

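### Section 9.5.1 takes the censoring date only from ePRO or paper-diary days, although scheduled contacts also collect positive-test status

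*Combined protocol and SAP*

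**What the plan says.** Section 9.5.1 lists the reasons for censoring as alternatives: stopping the spray, stopping ePRO entry, not handing in paper diaries, or not being reachable by telephone. Any such participant "will be censored on the day of their last ePRO clinical status submission or last available documented day on paper diary". A parenthesis then explains that date as the last day for which absence of a positive test was confirmed. No telephone, visit or early-termination date is named.

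Two further sentences bear on positives. One reads "Participants submitting a COVID-19 test result on or prior to Day 28 will be considered to have reached the primary endpoint", dated by specimen collection; it does not say by what route the result must arrive. The other censors at Day 28 those who submit results after Day 28.

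Section 6.6.2 has staff telephone all participants on Days 7 and 28, and those monitored remotely on Day 35 as well, to confirm "current health status including presence of any COVID-19 symptoms" and any ER or hospital visits due to COVID-19. In Table 4 (Appendix 1) the row "Report if tested positive for COVID-19 infection" is marked daily, at all three phone assessments and at early termination. The online or paper questionnaire is marked at the same contacts. The Day 28 assessment has a window of +2 days.

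**The concern.** The trial plans to ask about the primary endpoint at contacts that the censoring rule does not use. Read as written, a diary lapse is sufficient for censoring even when the participant answers the Day 28 call and reports no positive test. The days between the last diary entry and that call then leave the risk set, although they meet the rule's own description of confirmed status.

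For a positive reported at such a call the text gives two answers: censored before the specimen was taken, or an event on the specimen day. With about 12 expected events, one or two participants handled differently could matter. The conflict should be settled before data are seen.

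Diary lapse could also be related to falling ill, in which case a diary-only date would make the censoring more informative than it needs to be.

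**Working it through.** **The text applied to one participant.** Last diary entry on Day 10; reached at the Day 28 assessment.

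- Call on Day 28, no positive test, no questionnaire completed: censored at Day 10, and 28 − 10 = 18 days are dropped.
- The same call, and the participant also completes the scheduled questionnaire: there is now a Day 28 ePRO or paper date, and nothing is lost.
- Call on Day 28 reporting a positive with specimen on Day 15: the censoring sentence gives Day 10, censored; the event sentence gives Day 15, event.
- Call on Day 29 or 30 (inside the window) reporting the same Day 15 specimen: the sentence on results submitted after Day 28 can be read as censoring at Day 28.

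**Inputs, all from section 9.2.** Placebo hazard 0.000075 per day; HR 0.15; 5,740 per arm (11,480 ÷ 2); 25% censoring over 28 days; power claim "based on Cox regression model and a 2-sided 0.05-level test". The daily figure is used because it reproduces the stated events. It annualises to 0.000075 × 365 = 2.74%; 0.03/365 would give 13.2 events instead of 12.

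**Reproducing the plan.**
- Required events (Schoenfeld): 4(1.960 + 1.282)² / (ln 0.15)² = 11.68, rounded up to 12.
- Censoring hazard: c = −ln(0.75)/28 = 0.01027 per day.
- Expected events per arm: 5,740 × λ/(λ + c) × (1 − e^(−28(λ + c))). Placebo, λ = 0.000075: 10.46. NONS, λ = 0.15 × 0.000075: 1.57. Total 12.04, against the stated 10 + 2.
- Power: Φ(√(D/4) × |ln 0.15| − 1.96) with D = 12.04 gives 90.8%, against the stated 90%.

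The design reproduces.

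**Person-time affected by all censoring.** Mean follow-up is (1 − e^(−28c))/c = 0.25/0.01027 = 24.33 days. The loss is 3.67/28 = 13.1%, or about 42,100 of 11,480 × 28 = 321,440 person-days, among 0.25 × 11,480 = 2,870 participants.

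**What call data could recover.** With no censoring, expected events are 12.04 + 1.81 = 13.849, which is 1.81 more than with it. Let f be the share of the 25% that is diary lapse alone in participants who are reached and followed to Day 28. The documents do not give f, so a range is shown. Events = 12.04 + 1.81f.

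| f (assumed) | Expected events | Increase | Schoenfeld power |
|---|---|---|---|
| 0% | 12.0 | – | 90.8% |
| 10% | 12.2 | 1.5% | 91.2% |
| 25% | 12.5 | 3.8% | 91.8% |
| 50% | 12.9 | 7.5% | 92.7% |
| 100% (bound) | 13.8 | 15% | 94.2% |

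If only the Day 7 call succeeds, the most recovered per participant is 7 − (1 − e^(−7c))/c = 0.246 days, about 2,800 person-days in total and 0.1 event. Nearly all the gain comes from contacts at or after Day 28.

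**The case against.** The list of censoring reasons is loosely worded. Read literally, an ePRO user who hands in no paper diary already meets one of them, so it may be meant to describe people whose status is no longer obtained. Naming unreachability by telephone as a reason suggests that calls were expected to count. This stands as a point about intent, but the sentence fixing the date still admits only ePRO and paper.

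A reader might infer that a call can add a case but can never add case-free time. The documents do not support that. Table 4 schedules the questionnaire at each contact, section 3.1 has sites regularly collect paper diaries, and emergency contacts may submit data, so a contact can produce a usable date. A positive reported on Day 29 or 30 may, conversely, be read as censored at Day 28. What remains is that nothing tells staff to record the answer given at a call as a status date.

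A reader might also infer that all of the 25% censoring could be recovered. It could not: that figure is not broken down, and it includes participants who stop the spray and those who cannot be reached.

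Nor do the documents show bias. No text links diary lapse to illness, and no direction follows for a blinded 1:1 comparison. A diary-date rule is defensible, since one call credited with many undocumented days can miss or misdate a positive, and spray use cannot be documented once the diary stops.

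Sections 9.1 and 9.5.1 leave missing-data procedures to a separate SAP. No text reviewed here corrects the date rule, and the listed sensitivity analyses change the analysis set or the start of case counting, not the censoring date.

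**Conclusion.** The point holds in limited form. As written, section 9.5.1 gives no follow-up credit for a call confirming no positive test unless a questionnaire or diary entry accompanies it, and it has two conflicting sentences for a positive reported by call on or before Day 28 after the diary has stopped. The first departs from the rule's own explanation of the censoring date; the second must be reconciled whatever its frequency.

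The gain in precision is modest: 0.2 to 0.9 extra expected events and 0.4 to 1.9 percentage points of Schoenfeld power, assuming that 10% to 50% of the 25% censoring is diary lapse in participants reached to Day 28. The figure of 13.8 events is an unattainable bound. Informative censoring is a reason for care, not a demonstrated bias. This is a cheap improvement and does not undermine the stated sample size, which reproduces.

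**What to change.** In section 9.5.1:

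- Set the censoring date to the latest date, capped at Day 28, on which absence of a positive test was confirmed by any scheduled source: ePRO, paper diary, telephone or telehealth contact, site visit, early-termination assessment, or emergency contact.
- Remove diary lapse alone as a reason for censoring.
- Apply the same sources to positives, dated by specimen, so that both answers are handled alike. State explicitly how a specimen dated by Day 28 but reported later in the Day 28 window, or at Day 35, is treated.
- Have staff ask at each contact about any positive test since the last diary entry, with its specimen date, and record the status and date in the eCRF.
- Keep the diary-only date as a sensitivity analysis.

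The rule for participants who stop the spray is a separate matter and is unchanged here. The cost is wording, one question and a date field on contacts already scheduled. The drawback is recall over the days since the last diary entry, which the diary-only sensitivity analysis would help to gauge.

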2 STUDY OBJECTIVES AND ENDPOINTS

2.1 Primary Objective and Endpoint

Objective	Endpoint	
To assess the efficacy of NONS in the reduction of risk of COVID-19 infection	Confirmed positive COVID-19 test (Both antigen and SARS-CoV-2 RT-PCR are acceptable) by Day 28. Positive test results based on sample collection within 48 hours of randomization will be considered infected at randomization and not counted as events.	

Abbreviations: NONS=nitric oxide nasal spray; RT-PCR=real-time polymerase chain reaction.

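### Section 9.5.1 censors as event-free a positive swabbed by Day 28 but submitted later, and the already-infected exclusion runs from different dates in 2.1, 9.5.1 and 6.6.1

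*Combined protocol and SAP*

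**What the plan says.** **End of the counting window.** Section 2.1 and the synopsis define the primary endpoint as "Confirmed positive COVID-19 test (Both antigen and SARS-CoV-2 RT-PCR are acceptable) by Day 28". Section 9.5.1 then gives two adjacent rules. The first is "Participants who submit COVID-19 test results following Day 28, will be censored at Day 28". The second is "Participants submitting a COVID-19 test result on or prior to Day 28 will be considered to have reached the primary endpoint", with the event placed "on the day that the specimen (ie, nasal swab) is collected, not the date of the test". The sample-size text in Section 9.2, repeated in the synopsis, speaks of "preventing COVID-19 infections reported through 28 days". In Table 4 the row "Report if tested positive for COVID-19 infection" is marked at every contact from the daily diary to the last one, "End of Study 35±3". The last-treatment call has a window of Day 28 +2.

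**Start of the counting window.** The primary analysis will "count all cases occurring starting from the day after participants begin administering study treatment". In addition, positives close to randomization are treated as infections already present, under differing definitions:
- Section 2.1: the specimen was taken in the first 48 hours after randomization.
- Section 9.5.1 and the synopsis (Study Design): the result was obtained in that period.
- Section 6.6.1: the participant tests positive less than 2 days from the baseline visit, and is then unevaluable and discontinued.
- Section 7.12.2, on replacement: less than 2 days on study.

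**The concern.** A time-to-event endpoint needs one date that settles both whether an event falls in the window and when it happened. Section 9.5.1 uses two. A participant known to be infected before Day 28 can therefore enter the Cox model as uninfected at Day 28, only because the report arrived a day or two later.

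The secondary endpoint does not clearly share this limit. Section 9.5.2 dates it by the hospital or ER/ED day even where the positive came afterwards. A participant swabbed and admitted on Day 27, whose result is submitted on Day 29, can thus be a secondary event and yet event-free for the primary.

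At the start of the window, the same positive can be an event under one section and excluded under another. With 12 events planned, single cases carry weight, and a classification that two sections settle differently is open to dispute after unblinding. The listed sensitivity analyses vary only the analysis set and the start of counting, so none would show the effect of the submission cut-off.

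**Working it through.** **Inputs (Section 9.2).** Placebo daily hazard λ = 0.000075; HR 0.15; 11,480 participants 1:1, so n = 5,740 per arm; loss c = 0.0105 per day; two-sided 0.05. The documents give no swab-to-submission or swab-to-result times, so every lag below is an assumption.

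**1. Reproduce the plan.** Expected events per arm between days t0 and T:

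E = n·λ/(λ+c)·[exp(−(λ+c)·t0) − exp(−(λ+c)·T)], with 0.15λ in place of λ for NONS.

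For t0 = 0 and T = 28 this gives 10.43 placebo + 1.57 NONS = 12.00. Schoenfeld power = Φ(√D/2·|ln 0.15| − 1.96), which is 90.8% at D = 12. The plan's 12 events, 11,480 participants and 90% power are reproduced.

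**2. Apply the submission cut-off.** If a positive is submitted L days after the swab, only swabs taken up to Day 28 − L count, so T = 28 − L.

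| Lag L | Events, t0 = 0 | Lost | Power | Events, t0 = 1 | Power |
|---|---|---|---|---|---|
| 0 | 12.00 | – | 90.8% | 11.51 | 89.6% |
| 1 day | 11.63 | 0.37 (3.1%) | 89.9% | 11.14 | 88.6% |
| 2 days | 11.26 | 0.74 (6.2%) | 88.9% | 10.76 | 87.5% |
| 3 days | 10.88 | 1.12 (9.4%) | 87.9% | 10.39 | 86.4% |

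The t0 = 1 columns remove the first-dose day, as 9.5.1 does. The step from 12.00 to 11.51 comes from that rule; only the change down the column is due to the submission cut-off. The ratio of NONS to placebo events stays at 0.150 throughout, so equal lags leave the HR unbiased.

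**3. What one or two cases do.** With equal exposure the score statistic is z = (x − y)/√(x + y).
- 10 v 2: z = 8/√12 = 2.31, p = 0.021
- 9 v 2: z = 7/√11 = 2.11, p = 0.035
- 8 v 2: z = 6/√10 = 1.90, p = 0.058

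Suppose the true split by specimen date is 10 v 2 and each event is lost independently with probability 3.1%, 6.2% or 9.4%. The chance that the result reaches p ≥ 0.05 is then 3%, 11% or 20%.

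**4. The 48-hour exclusion.** Take first dose on the day of randomization, so that counting starts at about 24 h. A swab at 40 h with its result at 60 h is excluded under 2.1 (swab before 48 h) but can be an event under 9.5.1 (result after 48 h). The positives whose status changes are those swabbed between max(24 h, 48 h − result time) and 48 h. Putting these limits into the formula in step 1 gives 0.12, 0.24 or 0.49 expected events for result times of 6, 12 or 24 h. If counting starts 48 h or more after randomization, the number is zero.

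**The case against.** **The sentence may mean tests performed after Day 28.** On that reading it agrees with Section 2.1, and the paragraph is loosely drafted anyway: the sentence that follows does not even say the result must be positive. This may have been the intention. But that following sentence again makes submission by Day 28 the condition, and Section 9.2 also speaks of reporting. The text supports the literal reading, and if the other was meant, the fix simply states it.

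**It is an administrative cut-off that costs a little efficiency.** Correct when lags are equal between arms; no directional bias is claimed. Positives are reported daily and antigen tests count, so many lags may be short. A half-day lag leaves 11.8 events and 90.3% power.

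**The 10 v 2 split is fragile.** It is, and the 3%, 11% and 20% belong to it alone. By the same method 10 v 1 gives 0.02%, 0.2% and 0.9%, and 15 v 3 (18 cases, the closure number) stays below 1%. However, 10 v 2 is the split the plan itself expects.

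**The conflict with the secondary endpoint is not certain.** Section 9.5.2 follows the primary analysis, so the submission rule may carry over. That stands; the text permits the conflict without requiring it.

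**The exclusion wording is nearly editorial.** Baseline and randomization often coincide, and remote participants are sent drug overnight, which starts counting later and narrows the window. That limits the size. It does not remove the contradiction between 2.1 and 9.5.1.

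**A separate SAP may settle it.** Sections 9.1 and 9.5.1 do defer detail to one. Nothing in the documents available resolves either point.

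**Conclusion.** The concern holds on both parts. Section 9.5.1 as written discards true infections by Day 28 that the schedule collects, in conflict with the endpoint in Section 2.1. The already-infected exclusion is defined inconsistently, and no section has precedence.

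The size is modest: 0.4 to 1.1 of 12 expected events and about 1 to 3 points of power for assumed lags of 1 to 3 days. The exclusion wording adds 0.1 to 0.5 reclassified events, provided dosing starts on the day of randomization and results take 6 to 24 h. Bias in the HR would arise only if submission lags differed by arm. In a trial expected to be decided on 10 v 2 events this should be corrected, but it does not by itself undermine the design.

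**What to change.** In Section 9.5.1, count a positive as a primary event if all of these hold:
- its specimen was collected from the day after first dose through Day 28;
- it is not classed as infected at randomization;
- its specimen date precedes any earlier censoring under the existing rules of that section;
- it is reported by the end-of-study contact (Day 35±3).

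Date the event by specimen collection. Censor at Day 28 those still under observation with no positive specimen by then: participants never positive, and participants whose first positive specimen was taken later. The start-of-count and earlier-censoring rules stay as they are.

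Use one already-infected definition, a specimen collected within 48 h of randomization, in Section 2.1, Section 9.5.1 and the synopsis. Change the reporting-based phrase in Section 9.2 and the synopsis sample-size text to match. Sections 6.6.1 and 7.12.2 must be reconciled with this definition; no discontinuation or replacement rule is proposed here.

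The change is to wording. Dating events by specimen under 9.5.1 already requires the specimen date, and Table 4 already takes positive reports to the end-of-study contact. Neither Table 4 nor Appendix 3 shows a specimen-date field, so the team should confirm that the date is recorded for late reports as well. The cost is delay: the final count, and the running count for closing enrollment at 18 cases, can lag by up to about 10 days (Day 28 to Day 38).

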1.5 Nitric Oxide Nasal Spray Effects in Humans

The Sponsor has conducted Phase 1 and Phase 2 clinical trials to help establish the safety of NORS as a localized topical antimicrobial and further demonstrate the lack of a systemic toxicity signal as measured by methemoglobin. These trials also provide environmental safety data demonstrating that nitrogen dioxide (NO₂) levels remain below detection limits and far below Occupational Safety & Health Administration (OSHA) guidelines.

1.5.1 Nitric Oxide Nasal Spray (NONS) for the Treatment of Mild COVID-19 Infection Trial

In 2020, the Sponsor conducted a double-blinded, placebo-controlled trial that involved 79 adults diagnosed with mild COVID-19 in the community (confirmed by polymerase chain reaction [PCR]). Participants were randomly assigned to treatment with NONS or placebo (saline solution) at day 1. Nasal and throat swabs were collected at presentation for baseline followed by collection at Days 2, 4 and 6 which were 1, 3 and 5 days after starting treatment, respectively. Quantitative real-time reverse-transcriptase polymerase chain reaction (qRT-PCR) was performed to determine SARS-CoV-2 RNA. Nitric oxide nasal spray, started on or before day 5 of symptom onset, was independently associated with a significantly accelerated decrease in SARS-CoV-2 RNA concentration of -1.21 log₁₀ copies/ml on both Days 2 and 4, as compared to placebo. Therefore, the mean SARS-CoV-2 RNA concentration was lower for NONS, as compared to placebo, by a factor of 16 at both Days 2 and 4. Day 6 equated to at least 10 days since symptom onset and significant reduction of SARS-CoV-2 with or

without treatment was expected. Nevertheless, the SARS-CoV-2 RNA concentration was still lower on NONS at Day 6. The primary endpoint was a reduction of viral load from Day 1 through Day 6 (measured as area under the curve). Analysis revealed a mean difference of 5.22 log₁₀ copies/ml between NONS and placebo. This difference was shown to be significant with a P value of 0.0096. The average viral log reduction in the first 24 hours, in treatment arm was -1.362 which correlates to about 95%, while the average viral log reduction in the control (saline) arm was -0.15 which correlates to about 30% In addition, the majority of patients in this study were positive for SARS-CoV-2 variants of concern (VOC202012/01) also commonly known as the UK variant (European Medicines Agency 2020).

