9 PLANNED STATISTICAL METHODS

9.1 General Considerations

A detailed statistical analysis plan will be developed separately and finalized prior to randomization of the first participant. Deviations from the protocol-planned analyses will be noted.

The statistical analysis of the data obtained from this study will be performed using SAS® Version 9.4 or higher. All statistical tests will be performed at the 0.05 (two-sided) significance level, unless otherwise noted.

The data collected in this study will be documented using summary tables and participant data listings. Continuous variables will be summarized using descriptive statistics, specifically the number of observations, mean, median, standard deviation, minimum and maximum. Categorical variables will be summarized by frequencies and percentages. The analysis of both efficacy and safety parameters will be conducted for each treatment group separately. Active treatment will be compared against placebo.

Baseline characteristics will be summarized using descriptive statistics or frequencies and percentages, as appropriate. No statistical hypothesis tests will be performed on these characteristics.

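### The primary event is a positive nasal swab taken mostly while the nose is being sprayed with a virucide; reduced detection could contribute to a hazard ratio below 1, and no planned analysis looks at it

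*Combined protocol and SAP*

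**What the plan says.** The objective in section 2.1 is a lower risk of COVID-19 infection, and the endpoint is a positive antigen or RT-PCR test by Day 28. Section 9.5.1 dates the event at specimen collection: the participant has "reached the primary endpoint on the day that the specimen (ie, nasal swab) is collected". Section 5.2 has participants spray both nostrils three times daily for those 28 days.

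Testing is not scheduled. Section 6.6 relies on participants to say that they have tested positive, and the Schedule of Events (Appendix 1, Table 4) has a row "Report if tested positive for COVID-19 infection" that extends to the post-treatment follow-up contact. Section 9.5.1 then limits the analysis: "Participants who submit COVID-19 test results following Day 28, will be censored at Day 28". No section links the time of the swab to the time of the last spray.

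On the product's effect in infected people, section 1.5.1 reports that mean SARS-CoV-2 RNA in the sponsor's treatment trial was "lower for NONS, as compared to placebo, by a factor of 16 at both Days 2 and 4". The specimens were nasal and throat swabs, and the comparator was saline, as it is here.

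**The concern.** The drug acts at the site where the endpoint is measured. If it lowers the amount of virus on a swab from an infected person, that person may be less likely to test positive than an equally infected placebo participant. Randomization and blinding do not remove such a difference, because it would come from the drug's action on the measurement.

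The HR for detected positives would then mix two things: infections prevented and infections not detected. Section 9.2 treats them as one, reading an HR of 0.15 directly as 85% efficacy against infection. About 12 events are expected in all, so a few undetected NONS infections could change the result.

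The sensitivity analyses in section 9.5.1 change the stratification, the region or age group, the analysis set or the starting point. None bears on detection. The secondary endpoint is not an independent check either, because section 9.5.2 excludes hospitalized participants who test negative.

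**Working it through.** **Inputs.** From section 9.2: 5,740 participants per arm (11,480 / 2), placebo hazard λ = 0.000075 per day, loss c = 0.0105 per day, 28 days, HR 0.15, two-sided 0.05. From section 1.5.1: a fall of 1.21 log10 relative to saline. The detection ratios below are assumptions; the documents give no test sensitivity.

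**1. The plan's own figures.**
- Schoenfeld events: 4(1.960 + 1.282)² / (ln 0.15)² = 11.68, rounded up to 12.
- Placebo events: 5,740 × λ/(λ+c) × [1 − exp(−28(λ+c))] = 10.43.
- NONS events, with λ × 0.15: 1.57. The total is 12.00.
- Power at 12 events: Φ(√12 × 1.897/2 − 1.960) = 90.8%.

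The sample size and 90% power reproduce. The RNA factor also agrees: 10^1.21 = 16.2.

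**2. Reduced detection with no prevention (hypothetical).** Let r be the probability that a NONS infection is ever detected by Day 28, divided by the same probability on placebo. The apparent HR is r. Take Poisson counts with mean 10.4 for placebo (P) and 10.4r for NONS (N), and declare superiority when (P − N)/√(P + N) > 1.96.

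| r | Apparent HR | Apparent efficacy | Superiority declared |
|---|---|---|---|
| 1 | 1.00 | 0% | 2.6% |
| 0.75 | 0.75 | 25% | 8.9% |
| 0.50 | 0.50 | 50% | 25.5% |
| 0.25 | 0.25 | 75% | 59.3% |

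A second calculation fixes the event total and uses the binomial split. Significance needs at most 2 NONS events of 12, or at most 4 of 18. With half of NONS infections undetected, superiority is declared in 18% (12 events) or 23% (18 events) of trials; with 70% undetected, in 45% or 60%.

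**3. Mixture of both.** If half of NONS infections were undetected, an apparent efficacy of 85% would need a true efficacy of only 1 − 0.15/0.50 = 70%.

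**4. What Days 29-35 could add.** Assume testing continues as before and protection ends with the spray.
- Events per arm: 5,740 × λ/(λ+c) × [exp(−28(λ+c)) − exp(−35(λ+c))] = 2.16.
- With true efficacy of 85%, the Day 35 HR is (1.57 + 2.16)/(10.43 + 2.16) = 3.73/12.59 = 0.30. Power is Φ(√16.32 × 1.218/2 − 1.960) = 69%.
- In that week alone, with both arms at mean 2.16, NONS exceeds placebo by chance in about 40% of trials.
- Under heavy masking (85% undetected on spray, and undetected infections from the last 5, 7 or 10 spray days then surfacing), NONS would have about 3.6, 4.1 or 5.0 events against 2.2. The Day 35 HR would be about 0.41, 0.45 or 0.52. The power of the off-spray week alone is about 9% to 20%.

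**The case against.** Several stronger readings are tempting, and the documents do not support them.

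- *NONS is shown to make infected people test negative.* Section 1.5.1 reports RNA concentration in adults with confirmed mild disease, from nasal and throat swabs. It gives no proportion testing positive. The section 1.4 results are laboratory culture infectivity, whereas the endpoint is RNA or antigen.
- *Every counted swab is on spray, and the error always favours NONS.* The mITT set requires only one dose. Participants who stop are censored at their last status report, not their last spray. Testing is also prompted by participants, and section 7.4.4 lists cough, pharyngitis and headache as expected effects. If these differed by arm, they could prompt more testing on NONS. The direction is plausible, not certain.
- *The 26% and 59% are expected error rates.* They follow from assumed ratios. Repeat testing would shrink them: if per-swab detection were 40% against 80% and swabs were independent, two swabs give 64% against 96% (HR 0.67, about 13% declared superior). Three give 78% against 99% (HR 0.79, about 7%).
- *An excess of NONS positives after Day 28 would prove masking, so the efficacy claim should depend on it.* Such an excess occurs by chance in about 40% of trials of a product that works only while used.

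Part of the information is already collected: section 6.5 has participants record the date and time of each dose. The full diary content is in a Manual of Procedures, and further detail is left to a separate SAP; neither is available here. The endpoint is also openly described as a positive test.

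What remains is that the documents in hand contain no rule on swab timing and no analysis directed at differential detection, and that reported off-spray positives are left out.

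**Conclusion.** The point holds as a limit on interpretation and a cheap improvement. It is not a demonstrated bias. The mechanism is credible on the sponsor's own data, and nothing listed in the plan examines it. Its size is unknown: detection ratios of 0.75 to 0.25 with no true prevention give apparent efficacy of 25% to 75% and false superiority in about 9% to 59% of trials. These figures rest on the design rate, the assumed ratios and Poisson counts.

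Days 29-35 can help show masking but cannot settle it. No test is scheduled, few events are expected, and adding the week more than doubles the expected NONS events (1.57 to 3.73) even when the product works.

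**What to change.** Leave the Day 28 primary analysis, sample size and dosing as they are.

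1. In the participant instructions and section 6.6, ask that a COVID-19 swab be taken, where feasible, before rather than after a scheduled spray. Record specimen collection time, specimen site and test type with each reported result, unless the Manual of Procedures already does so. This reduces immediate interference at the swab. It does not remove a sustained fall in viral load.
2. In section 9.5.1, tabulate by arm the positives with specimen dates in Days 29-35. Add a supportive Cox analysis by specimen date to Day 35. Label both descriptive, and do not make the efficacy claim conditional on them.
3. In the planned interpretation, state that the endpoint is a positive test obtained largely while on spray, and that reduced detection cannot be excluded as part of any effect.

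The cost is one instruction, up to three data fields and one extra analysis of reports already scheduled to Day 35. The drawback is dilution: about 2.2 off-spray events per arm would move the HR from 0.15 to about 0.30, and power from about 91% to about 69%, under a true efficacy of 85% that ends at Day 28. The text should say so, so that a weaker Day 35 result is not read as evidence of masking by itself.
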